**Figure JAIY.6.1. Illustration of graphical multiple testing procedure with initial  $\alpha$  allocation and weights.**

For Japan, the same testing strategy will be used, however, the proportion of patients achieving EASI75 and IGA of 0 or 1 at Week 16 are considered co-primary. Both endpoints have to meet statistical significance compared with placebo in order to demonstrate a superiority of a given baricitinib dose (baricitinib 4-mg and/or baricitinib 2-mg) compared with placebo.

There will be no adjustment for multiple comparisons for any other analyses.

### 6.7. Patient Disposition

An overview of patient populations will be summarized by treatment group. Frequency counts and percentages of patients excluded prior to randomization by primary reason for exclusion will be provided for patients who failed to meet study entry requirements during screening.

Patient disposition through Week 16 will be summarized using the ITT population. Frequency counts and percentages of patients who complete the study treatment visits or discontinue early from the study along with whether they completed follow-up, did not complete follow-up or

enrolled into the extension will be summarized separately by treatment group for patients who are not rescued and for patients who are rescued, along with their reason for study discontinuation. Frequency counts and percentages of patients who complete the treatment or discontinue treatment early will also be summarized separately by treatment group for patients who are not rescued and for patients who are rescued, along with their reason for treatment discontinuation.

A listing of patient disposition will be provided for all randomized patients, with the extent of their participation in the study and the reason for discontinuation. A listing of all randomized patients with their treatment assignment will also be provided.

## 6.8. Patient Characteristics

Patient characteristics including demographics and baseline characteristics will be summarized descriptively by treatment group for the ITT population. Historical illnesses and pre-existing conditions will be summarized descriptively by treatment group for the ITT population. No formal statistical comparisons will be made among treatment groups unless otherwise stated.

### 6.8.1. Demographics

Patient demographics will be summarized as described above. The following demographic information will be included:

- Age
- Age group (<65 vs. ≥65)
- Age group (<65, ≥65 to <75, ≥75 to <85, ≥85)
- Gender (male, female)
- Race (American Indian or Alaska Native, Asian, Black or African American, Native Hawaiian or Other Pacific Islander, White, Multiple)
- Region (as defined in [Table JAIY.5.1](#))
- Country
- Weight (kg)
- Weight category (<60 kg, ≥60 to <100 kg, ≥100 kg)
- Height (cm)
- BMI (kg/m^2)
- BMI category (<25 kg/m^2, ≥25 to <30 kg/m^2, ≥30 kg/m^2)

A listing of patient demographics will also be provided for the ITT population.

### 6.8.2. Baseline Disease Characteristics

The following baseline disease information will be categorized and presented for baseline AD clinical characteristics, baseline health outcome measures, and other baseline demographic and disease characteristics as described above:

- Duration since AD diagnosis (years)
- Duration since AD diagnosis category (0 to <2 years, 2 to <5 years, 5 to <10 years, 10 to <20 years, ≥20 years)

- Age at Diagnosis (years)
- Age Group at Diagnosis (<18 years, ≥18 to <50 years, ≥50 years)
- Habits (Alcohol: Never, Current, Former; Tobacco: Never, Current, Former)
- Skin Infections treated with a pharmacological agent within past year (yes, no, unknown; number if yes)
- Atopic Dermatitis Flares within past year (yes, no, unknown; number if yes)
- Validated Investigator's Global Assessment for AD (IGA) score
- Eczema Area and Severity Index (EASI) score
- SCORing Atopic Dermatitis (SCORAD)
- Body Surface Area (BSA) affected by AD
- Hospital Anxiety Depression Scale (HADS) subscales
- Patient-Oriented Eczema Measure (POEM)
- Itch Numerical Rating Scale (NRS)
- Atopic Dermatitis Sleep Scale (ADSS) Item 2
- Dermatology Life Quality Index (DLQI)
- Skin Pain NRS
- Patient Global Impression of Severity (PGI-S-AD)
- Prior therapy (topical therapy only; systemic therapy)
- Prior use of Cyclosporine (yes, no)
- Cyclosporine inadequate response (yes, no)
- Cyclosporine intolerance (yes, no)
- Cyclosporine contraindication [ineligible] (yes, no)
- Cyclosporine inadvisable (yes no)
- Prior use of TCNI (yes, no)
- TCNI inadequate response (yes, no)
- TCNI intolerance (yes, no)
- TCNI contraindication [ineligible] (yes, no)
- TCNI inadvisable (yes, no)
- Vaccine (yes, no)
- Baseline renal function status: impaired (eGFR <60 mL/min/1.73 m^2) or not impaired (eGFR ≥60 mL/min/1.73 m^2)
- Immunoglobulin E (IgE): intrinsic(<200 kU/I) or extrinsic (≥200 kU/I)

### **6.8.3. Historical Illness and Pre-existing Conditions**

Historical illnesses are defined as those conditions recorded in the Pre-existing Conditions and Medical History electronic case report form (eCRF) or from the Prespecified Medical History: Comorbidities eCRF with an end date prior to the informed consent date. The number and percentage of patients with selected historical diagnoses will be summarized by treatment group using the ITT population. Historical diagnoses will be categorized using the Medical Dictionary for Regulatory Activities (MedDRA®, most current available version) algorithmic standardized MedDRA queries (SMQs) or similar pre-defined lists of preferred terms (PTs) of interest.

Preexisting conditions are defined as those conditions with a start date prior to the first dose of the study drug and stop dates that are at or after the informed consent date or have no stop date

(i.e., are ongoing). For events occurring on the day of the first dose of study treatment, the date and time of the onset of the event will both be used to determine if the event was pre-existing. Conditions with a partial or missing start date (or time if needed) will be assumed to be ‘not pre-existing’ unless there is evidence, through comparison of partial dates, to suggest otherwise. Pre-existing conditions will be categorized using the MedDRA SMQs or similar pre-defined lists of PTs of interest. Frequency counts and percentages of patients with selected pre-existing conditions will be summarized by treatment group using the ITT population.

## 6.9. Treatment Compliance

Patient compliance with study medication will be assessed from Week 0 (Visit 2) to Week 16 (Visit 8) or Early Termination using the ITT population.

All patients are expected to take 2 tablets daily from a package as described in the protocol. Each bottle contains 36 tablets. A patient is considered noncompliant if he or she misses >20% of the prescribed doses during the study, unless the patient’s study drug is withheld by the investigator. For patients who had their treatment temporarily interrupted by the investigator, the period of time that dose was withheld will be taken into account in the compliance calculation.

Compliance in the period of interest up to Visit  $x$  will be calculated as follows:

$$\text{Compliance} = \frac{\text{total number of tablets dispensed} - \text{total number of tablets returned}}{\text{expected number of total tablets}}$$

where

- Total number of tablets dispensed: sum of tablets dispensed in the period of interest prior to Visit  $x$ ;
- Total number of tablets returned: sum of the tablets returned in the period of interest prior to and including Visit  $x$ ;
- Expected number of tablets: number of days in the period of interest\*number of tablets taken per day = [(date of last dose – date of first dose + 1) – number of days of temporary drug interruption]\*number of tablets taken per day

Patients who are significantly noncompliant (compliance <80%) through Week 16 will be excluded from the PPS population.

Descriptive statistics for percent compliance and non-compliance rate will be summarized for the ITT population by treatment group for Week 0 through Week 16. Sub-intervals of interest, such as compliance between visits, may also be presented. The number of expected doses, tablets dispensed, tablets returned, and percent compliance will be listed by patient for Week 0 through Week 16.

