eGFR <40 mL/min/1.73 m ² (from serum creatinine) for patients with screening eGFR ≥ 60 mL/min/1.73 m ²	eGFR ≥ 50 mL/min/1.73 m ²
eGFR <30 mL/min/1.73 m ² (from serum creatinine) for patients with screening eGFR ≥ 40 to <60 mL/min/1.73 m ²	eGFR ≥ 40 mL/min/1.73 m ²
ALT or AST >5x ULN	ALT and AST return to <2x ULN, and IP is not considered to be the cause of enzyme elevation
Hemoglobin <8 g/dL (<80.0 g/L)	Hemoglobin ≥ 10 g/dL (≥ 100.0 g/L)
Symptomatic herpes zoster	All skin lesions have crusted and are resolving
Infection that, in the opinion of the investigator, merits the IP being interrupted	Resolution of infection
Clinical features of VTE (such as deep vein thrombosis or pulmonary embolism) are present ^a	After evaluation and institution of appropriate treatment of VTE ^b

Abbreviations: ALT = alanine aminotransferase; ANC = absolute neutrophil count; AST = aspartate aminotransferase; eGFR = estimated glomerular filtration rate; IP = investigational product; ULN = upper limit of normal; VTE = venous thromboembolic event; WBC = white blood cell.

- a Evaluate promptly and institute appropriate treatment. Upon evaluation if VTE is ruled out and no other temporary or permanent discontinuation criteria are met, then IP may be resumed.
- b After evaluation and institution of treatment if the investigator deems that the patient is still at significant risk, or if this would constitute a second VTE for the patient, then IP should be discontinued permanently.

Although temporary interruption of investigational product is not a requirement at times of increased potential risk of VTE (e.g., surgery, significant air travel, or other situations involving prolonged immobilization) we recommend following appropriate VTE prophylaxis guidelines to help manage the VTE risk under these circumstances.

For specific guidance on temporary interruption of investigational product after use of a prohibited medication, please refer to Section 7.7.3 (Prohibited Medications and Procedures).

Lastly, investigational product should be temporarily interrupted for suicidal ideation or any suicide-related behaviors as assessed by the following patient responses on the C-SSRS:

- A “yes” answer to Question 4 (Active Suicidal Ideation with Some Intent to Act, Without Specific Plan) **or**
- A “yes” answer to Question 5 (Active Suicidal Ideation with Specific Plan and Intent) on the “Suicidal Ideation” portion of the C-SSRS **or**

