#### 6.2.1. Analysis Populations

**Intent-to-treat (ITT) population:** The ITT population analysis set is defined as all randomized patients.

**Per-protocol Set (PPS):** PP subset of the ITT analysis set will include those patients who do not have any significant or important protocol violations. Qualifications for and identification of

significant or important protocol violations will be determined while the study remains blinded, prior to database lock.

**Follow-up population:** The follow-up population is defined as patients who entered the follow-up period.

Unless otherwise specified, the efficacy and health outcome analyses will be conducted on the ITT population (Gillings and Koch 1991), which seeks to preserve the benefits of randomization and avoid selection bias. Patients will be analyzed according to the treatment to which they were randomized. In addition, the analyses of primary and key secondary endpoints will be repeated using the PPS population.

**Safety population:** The safety population is defined as all randomized patients who receive at least 1 dose of investigational product and who did not discontinue from the study for the reason 'Lost to Follow-up' at the first postbaseline visit.

Safety analyses will be performed using the safety population. Patients will be analyzed according to the treatment regimen to which they were assigned. Analyses of the safety endpoints, many of which are incidence based, will include all patients in the safety population, unless specifically stated otherwise.

In the rare situation where a patient is Lost to Follow-up at the first postbaseline visit, but some safety data exists (e.g., unscheduled laboratory assessments) after first dose of study drug, a listing of the data or a patient profile may be provided, when requested.

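### The SAP 6.9 compliance formula does not limit interruption days to those between first and last dose, so a hold with no later dose can be deducted twice

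*SAP*

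**What the plan says.** SAP Section 6.9 defines compliance as tablets dispensed minus tablets returned, divided by expected tablets. Expected tablets are introduced as "number of days in the period of interest" times tablets per day. This is then written out as the span "date of last dose – date of first dose + 1", less the interruption days: "number of days of temporary drug interruption]\*number of tablets taken per day". The daily number is two: "All patients are expected to take 2 tablets daily from a package as described in the protocol".

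The section states its intent for patients interrupted by the investigator: "the period of time that dose was withheld will be taken into account in the compliance calculation". It also exempts doses withheld by the investigator from its definition of noncompliance. The rule for the per-protocol set, however, is a plain numeric cut: "Patients who are significantly noncompliant (compliance <80%) through Week 16 will be excluded from the PPS population". SAP Section 6.2.1 gives that set its role: "the analyses of primary and key secondary endpoints will be repeated using the PPS population".

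The protocol allows for holds that are not followed by another dose. In Table JAIY.4 (Protocol 8.1.1), resumption after an ALT or AST hold requires that "ALT and AST return to <2x ULN, and IP is not considered to be the cause of enzyme elevation". A note to the same table lets a hold for venous thromboembolism become permanent, and Protocol 7.7.3 does so for probenecid. Protocol 7.7.3 also sets a 12-week hold after BCG vaccination, within a 16-week treatment period.

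**The concern.** The span in the formula already stops at the last tablet taken. Deducting interruption days is right when dosing resumes, because the hold then lies inside the span. When no dose follows the hold, the withheld days are already outside the span, and nothing in the formula keeps them from being deducted again. The denominator is then too small, zero or negative.

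Two outputs are at stake. The by-patient listing and by-group compliance summaries could carry wrong or impossible values. The 80% cut could also place some patients on the wrong side of the per-protocol set, on which the primary and key secondary analyses are repeated as sensitivity analyses.

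**Working it through.** The documents state no compliance figure to reproduce, so the check is arithmetic on the formula.

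**Inputs**
- Expected tablets = [(last dose − first dose + 1) − interruption days] × 2 (SAP 6.9).
- PPS cut: compliance below 80% is excluded. SAP 6.9 gives no upper cut.
- Treatment period: 16 weeks = 112 days (Protocol 5.1.2).
- L = days from first to last dose, with no hold inside; I = hold days after the last dose; c = true compliance over the L days. The values of L, I and c below are illustrations, not data from the documents.

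**Formula**

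Tablets taken = 2cL. If the I days are deducted, expected tablets = 2(L − I), so computed compliance = c × L/(L − I). If they are not deducted, computed compliance = c.

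**A resumed hold is handled correctly.** For a 112-day span with a 14-day hold inside it, expected tablets = (112 − 14) × 2 = 196. A patient who took 196 has 100%.

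**A hold with no later dose**

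| L | I | True c | Taken | Expected if I is deducted | Computed | Expected if I is not deducted |
|---|---|---|---|---|---|---|
| 80 | 14 | 70% | 112 | 132 | 84.8% | 160 (70%) |
| 84 | 28 | 100% | 168 | 112 | 150% | 168 (100%) |
| 56 | 56 | 100% | 112 | 0 | undefined | 112 (100%) |
| 40 | 72 | 100% | 80 | −64 | −125% | 80 (100%) |
| 28 | 84 | 100% | 56 | −112 | −50% | 56 (100%) |

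The last row is what a 12-week hold (84 days) starting on Day 29 would give.

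**When PPS membership changes**
- *Wrongly kept:* this needs c < 80%, I < L and c × L/(L − I) ≥ 0.8, that is, I/L ≥ 1 − c/0.8. The smallest I/L is 6.25% for c = 75%, 12.5% for c = 70% and 25% for c = 60%. In the first row I/L = 14/80 = 17.5%, which exceeds 12.5%, so that patient is kept.
- *Wrongly excluded:* this needs c ≥ 80% and I > L. The value is then negative and fails the numeric cut. At I = L it is undefined, and the SAP has no rule for that.
- *No change:* a patient at 80% or above with I < L has an inflated value but stays in the set.

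**The case against.** The best defence is that the text, read sensibly, already excludes these days. The SAP never says that all interruption days are deducted. The bracket is introduced as a number of days in the period of interest, which cannot be negative. The days are called temporary, whereas the protocol treats permanent discontinuation separately (8.1.1 and 8.1.2), as does SAP 6.15.2.3. A hold that becomes a permanent stop may therefore never be coded as temporary.

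Part of this stands. For a hold that turns into a permanent stop, double deduction depends on a recording convention that the documents do not give. It does not settle the matter, though. Section 6.9 takes the period of interest up to a visit and assesses compliance to Week 16 or Early Termination, so that period can contain withheld days after the last dose. A hold still open at Week 16 is also still temporary.

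Safeguards exist. Compliance is listed by patient (6.9), violations are identified while the study is blinded (6.2.1), and deviations go to review meetings under a separate plan not among the documents here (6.17). A negative value should be noticed. An inflated one such as 84.8% looks ordinary and is less likely to be.

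The exemption for doses withheld by the investigator also counts. A patient who took every dose before the hold is not meant to be noncompliant. But the PPS sentence applies the computed percentage and does not repeat the exemption.

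A reader might infer that the formula is wrong for every interruption, that the per-protocol set is certainly misassigned, or that the errors differ between arms. The documents support none of these. Resumed holds are computed correctly, misassignment needs the conditions derived above, and nothing is given on how often such holds occur or in which arm. Nor do the errors fall only on safety stops, since holds also follow prohibited medication.

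**Conclusion.** The point holds as a gap in a stated formula. As written, Section 6.9 permits a hold with no later dose to be deducted twice, and the result is then wrong by the factor L/(L − I). This rests on one assumption: that such hold days are recorded as temporary interruption and entered in the formula without a date limit. The SAP neither requires nor prevents this.

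The consequence is small. It reaches the compliance summaries and listing and the per-protocol sensitivity analyses. The intent-to-treat primary analysis does not use compliance. The number of patients affected cannot be computed from the documents and is probably small, because a hold must run to the end of the patient's dosing and must also meet one of the membership conditions.

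**What to change.** In SAP 6.9, define the subtracted term as: *number of days of temporary drug interruption falling between the first and last dose dates in the period of interest*. Apply the same rule to compliance computed up to each visit and between visits, where a hold open at the visit raises the same question. The rule returns true compliance in every row of the table and leaves resumed holds unchanged. The cost is one clause in the SAP and one programming condition, with no new data.

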7.1.1. Packaging and Labeling

The sponsor (or its designee) will provide the following investigational products:

- tablets containing 4-mg of baricitinib
- tablets containing 2-mg of baricitinib
- placebo tablets to match baricitinib 4-mg tablets and 2-mg tablets

Patients are required to take 2 tablets daily from packages assigned by the IWRS.

Clinical trial materials will be labeled according to the country's regulatory requirements.

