7.6. Treatment Compliance

Patient compliance with study medication will be assessed at each visit during the treatment period (Visit 3 through Visit 8) by counting returned tablets.

A patient will be considered significantly noncompliant if he or she misses more than 20% of the prescribed doses of investigational product during the study, unless the patient's investigational product is withheld by the investigator for safety reasons. Similarly, a patient will be considered significantly noncompliant if he or she is judged by the investigator to have intentionally or repeatedly taken 20% more than the prescribed amount of medication during the study.

Patients will be counseled by study staff on the importance of taking the investigational product as prescribed, as appropriate.

Patients' compliance will be further defined in the statistical analysis plan (SAP).

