10.3.2.4. Treatment Compliance

Treatment compliance with the randomly assigned study medication will be evaluated at every clinic visit through the counts of returned investigational product tablets. A patient will be considered significantly noncompliant if he or she misses more than 20% of the prescribed doses during the study, unless the patient's investigational product is withheld by the investigator for safety reasons; that is, compliance <80%. Similarly, a patient will be considered significantly noncompliant if he or she is judged by the investigator to have intentionally or repeatedly taken more than the prescribed amount of medication, that is, compliance $\geq 120\%$.

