### 6.17. Protocol Deviations

Protocol deviations will be tracked by the clinical team, and their importance will be assessed by key team members during protocol deviation review meetings. Out of all important protocol deviations (IPDs) identified, a subset occurring during Period 2 with the potential to affect efficacy analyses will result in exclusion from the PP population.

Potential examples of deviations include patients who receive excluded concomitant therapy, significant non-compliance with study medication (<80% of assigned doses taken, failure to take study medication and taking incorrect study medication), patients incorrectly enrolled in the study, and patients whose data are questionable due to significant site quality or compliance issues. Refer to a separate document for the important protocol deviations.

Trial Issue Management Plan includes the categories and subcategories of important protocol deviations and whether or not these deviations will result in the exclusion of patients from per protocol set.

The number and percentage of patients having IPD(s) will be summarized within category and subcategory of deviation by treatment group for Period 2 using the ITT population. Individual patient listings of IPDs will be provided. A summary of reasons patients were excluded from the PPS will be provided by treatment group.

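### The SAP keeps only the under-use half of the protocol's definition of significant noncompliance, so over-users are missing from the reported rate and from the per-protocol exclusion in SAP 6.9

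*SAP*

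**What the plan says.** Protocol section 7.6 gives two routes to significant noncompliance. A patient meets the first if "he or she misses more than 20% of the prescribed doses of investigational product during the study", apart from drug withheld by the investigator for safety. A patient meets the second if the investigator judges that the patient has "intentionally or repeatedly taken 20% more than the prescribed amount of medication during the study". Protocol section 10.3.2.4 repeats both and attaches percentages: under 80% for the first, and for the second "intentionally or repeatedly taken more than the prescribed amount of medication, that is, compliance" of 120% or more. Section 7.6 leaves further definition of compliance to the SAP.

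SAP section 6.9 defines noncompliance only as missing more than 20% of doses. Its rule for the per-protocol set is: "Patients who are significantly noncompliant (compliance <80%) through Week 16 will be excluded from the PPS population". Compliance is tablets dispensed minus tablets returned, divided by the tablets expected at two per day, with all tablets in one total. Percent compliance and the noncompliance rate are summarised by arm, and each patient's figures are listed.

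SAP section 6.17 offers potential examples of deviations and describes significant non-compliance as "<80% of assigned doses taken, failure to take study medication and taking incorrect study medication". Over-use is not named. The section refers to a Trial Issue Management Plan for the categories that lead to PPS exclusion. Under SAP section 6.2.1, violations are settled blinded before database lock, and the primary and key secondary analyses are repeated in the PPS.

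**The concern.** The two documents define the same term differently. A patient whom the investigator judges to have repeatedly over-used study drug, with compliance of 120% or more, is significantly noncompliant under the protocol and compliant under SAP 6.9. The protocol lets the SAP add detail, but nothing in SAP 6.9 or 6.17 says that half of the definition was dropped on purpose, or why.

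Two outputs are affected. The noncompliance rate by arm would not be the rate that the protocol defines. The PPS rule in 6.9 would remove marked under-users and no over-users, although the PPS repeat is meant to describe patients without important departures from the plan.

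Two features of the formula add to this on a smaller scale. It does not separate tablet sizes, and it counts every tablet that is not returned as taken.

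**Working it through.** **Limits.** Missing more than 20% means compliance below 1 − 0.20 = 80%. Taking 20% more means 1 + 0.20 = 120%. Protocol 7.6 and 10.3.2.4 therefore agree with each other. SAP 6.9 keeps the first limit and has no ceiling.

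**Inputs.** Treatment lasts 112 days (Protocol Schedule of Activities) at two tablets per day (Protocol 7.1.1, SAP 6.9), so 112 × 2 = 224 tablets are expected. In the active arms the two tablets are one active and one placebo matching the other strength (Table JAIY.3), so pooled compliance = (active tablets + dummy tablets)/224. Bottles hold 36 tablets (SAP 6.9). The number of bottles per visit is not stated.

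**Over-use.**
- Both tablets at 120%: 2 × 1.2 × 112 = 268.8; 268.8/224 = 120%. At the protocol's figure; not flagged by SAP 6.9.
- Both tablets at 150%: 336/224 = 150%. Above the protocol's figure; not flagged by SAP 6.9.
- Such values are feasible if two bottles (one per tablet size) are dispensed at each of the six dispensing visits (assumption): 6 × 72 = 432 tablets, so at most 432/224 = 193%. One bottle per visit gives 216 tablets, which does not cover the 224 expected.

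**Pooling of tablet sizes.**
- 60% of active, 100% of dummy: (67.2 + 112)/224 = 179.2/224 = 80%. Not below 80%, so passes.
- 50% of active, 100% of dummy: (56 + 112)/224 = 75%. Flagged.
- If the dummy is not over-taken, a patient who passes has therefore taken at least 60% of the active tablets.
- 120% of active, 100% of dummy: (134.4 + 112)/224 = 110%. A pooled limit of 120% would not show this either.

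**Unreturned bottles** (assuming one 36-tablet bottle per tablet size per visit). An unreturned Week 0–1 supply counts 72 tablets against 14 expected, an excess of 58.
- Patient who took every dose: (224 + 58)/224 = 282/224 = 126%.
- Patient truly at 60%: (0.6 × 210 + 72)/224 = 198/224 = 88%, which passes.

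**Power.** Exact enumeration of the two-sided Fisher test with 100 per arm, 10% against 30% and alpha 0.025 gives 0.891, matching the stated 89%. It rests on all randomised patients and does not involve the PPS.

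**The case against.** The strongest reply is that little follows from the omission. The PPS is used only for sensitivity analyses. The protocol does not define a PPS, so SAP 6.9 breaks no protocol rule on who belongs in it. Over-use is not hidden, because each patient's percent compliance is listed. SAP 6.17 is open-ended, and its examples include taking incorrect medication. All of this stands, and it limits the size of the point. It does not remove the mismatch: a listing shows a value of 130% but neither counts that patient as noncompliant nor says what follows for the PPS.

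A reader might infer several stronger things that the documents do not support.

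- *Over-users stay in the PPS.* This cannot be known. SAP 6.17 and the Trial Issue Management Plan give another route to exclusion. One can say only that the 6.9 rule does not remove them.
- *Patients on double or no active drug for 16 weeks would show 100% compliance.* Under the one-bottle-per-size assumption, with leftovers returned at each visit, intervals of 7, 7, 14, 28, 28 and 28 days at two tablets a day from one bottle yield at most 14 + 14 + 28 + 36 + 36 + 36 = 164 tablets. 164/224 = 73%, which SAP 6.9 already excludes. Very low active intake passes only with matching over-use of the dummy: 164 dummy tablets (146%) plus 15.2 active tablets (14%) reaches 179.2/224 = 80%. That is an arithmetical limit, not an expected pattern.
- *A full complier with an unreturned supply (126%) is noncompliant under the protocol.* The protocol requires an investigator's judgement of intentional or repeated over-use. A count alone does not meet it.
- *Restoring the 120% limit would expose masked under-use.* It would not: the 80% and 88% cases lie below it.
- *Pooling tablet sizes departs from the protocol.* The protocol also counts returned tablets without separating sizes. In the placebo arm both tablets are placebo, so pooling hides no error in active drug there.

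**Conclusion.** The protocol and SAP disagree on the meaning of significant noncompliance. SAP 6.9, and the examples in 6.17, drop the investigator-judged over-use category without explanation. As written, the noncompliance rate covers one side only, and the 6.9 rule takes no over-user out of the PPS. This rests on the text of both documents and needs no assumption.

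The pooled count and the treatment of unreturned bottles are smaller weaknesses of the formula. The 60%/100% case follows from the formula and the double-dummy regimen alone. The 126% and 88% cases depend on the assumed two bottles per visit.

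The reach is limited to compliance reporting and the PPS sensitivity analyses. The ITT primary analysis and the 89% power are unchanged. The documents give no basis for estimating how many patients are affected or how far any PPS result would move.

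**What to change.** In SAP 6.9, define significant noncompliance as in Protocol 7.6 and 10.3.2.4: compliance below 80%, or compliance of 120% or more together with the investigator's judgement of intentional or repeated over-use. Report the rate overall and for each side by arm. Apply the over-use category to PPS exclusion in the same way as the under-use category, and name it in SAP 6.17. If the sponsor means to leave it out, the SAP should say so and give the reason.

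As supporting checks, if bottle-level counts are recorded (an assumption), report compliance by tablet size beside the pooled figure. Also add a rule that tablets in unreturned bottles are not counted as taken. SAP 6.11.1 already has a rule for unreturned topical corticosteroid tubes, including leaving out those of unknown use; SAP 6.9 has none for study drug.

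The cost is a few lines of SAP text and one more derivation. The PPS may lose a few patients. The classification can be made blinded before database lock, when SAP 6.2.1 already settles PPS membership.
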